Protocol Number SCTA01-B301

A Multicenter, Adaptive, Randomized, Double-blinded, Placebo-controlled Phase II/III Trial to Evaluate the Efficacy and Safety of Monoclonal Antibody SCTA01 against SARS-CoV-2 in Hospitalized Patients with Severe COVID-19

Investigational Product Number:	SCTA01
Investigational Product Name:	Recombinant anti-SARS-CoV-2 spike protein monoclonal antibody
United States (US) IND Number:	IND 152456
Sponsor Contact (Medical):	[contact] [contact]
Sponsor Contact (Study Operations):	[contact] [contact]
SAE Reporting:	Submit SAE Reports to: [contact] , CC: [contact]

Protocol Version	Date
3.0	07 January 2021
4.0	02 July 2021
5.0	24 Aug 2021

PROTOCOL SYNOPSIS

Name of Sponsor/Company: Sinocelltech, Ltd.
Name of Investigational Product: Recombinant anti-SARS-CoV-2 spike protein monoclonal antibody (Product Code: SCTA01)
Name of Active Ingredient: Recombinant humanized anti-SARS-CoV-2 monoclonal IgG1 antibody (SCTA01)
Title of Study: A multicenter, adaptive, randomized, double-blinded, placebo-controlled Phase II/III trial to evaluate the efficacy and safety of monoclonal antibody SCTA01 against SARS-CoV-2 in hospitalized patients with severe COVID-19
Study Number: SCTA01-B301
Study Phase: Phase II/III
Study Population: Hospitalized patients with severe COVID-19 (5 point on the 8-point ordinal scale). According to the NIH definition, severe patients are those individuals who have one of the following: 1) respiratory rate > 30 breaths per minute; 2) pulse oxygen saturation (SpO_2) $\leq 93\%$ on room air at sea level; 3) $PaO_2/FiO_2 < 300$ mmHg or $SpO_2/FiO_2 \leq 315$ mmHg; 4) lung infiltrates > 50%. 5 point: Hospitalized, requiring supplemental oxygen.
Primary Objectives: 
● To evaluate the clinical efficacy of SCTA01 as assessed by time to clinical improvement (Phase II, III).
Secondary Objectives: 
● To evaluate the clinical efficacy of SCTA01 as assessed by clinical severity, hospitalization and mortality (Phase II, III);● To evaluate the safety of SCTA01 (Phase II, III);● To evaluate the virologic efficacy of SCTA01 (Phase II, III);● To evaluate the pharmacokinetics of SCTA01 (Phase II);● To evaluate the immunogenicity of SCTA01 (Phase II, III).

Exploratory Objectives:

- To explore the correlation between the baseline serological antibody level and therapeutic effect (Phase II, III);
- To evaluate the virologic efficacy of SCTA01 as assessed by quantitative SARS-CoV-2 virus in patient's blood (Phase II, III).

Primary Endpoints:

- Time to clinical improvement (TTCI) up to Day 29. TTCI is defined as the time (in days) from randomization to the first day on which a patient satisfies point 1, 2, or 3 on the 8-point ordinal scale and maintains a score ≤ 3 at least 48 hours (initial improvement) and maintains this up to Day 29 (sustained improvement) (Phase II, III).

Secondary Endpoints:

- Clinical efficacy of SCTA01:
 - Proportion of patients with initial clinical improvement at Day 29 (Phase II, III);
 - Proportion of patients with sustained clinical improvement at Day 29 (Phase II, III);
 - Time to initial clinical improvement up to Day 29 (Phase II, III);
 - Time to discharge from hospital, followed by being alive and home for 14 consecutive days prior to Day 90 (Phase II, III);
 - Proportion of patients discharged from hospital, followed by being alive and home for 14 consecutive days prior to Day 90 (Phase II, III);
 - All-cause mortality up to Day 29, record date and cause of death (if applicable) (Phase II, III);
 - Percentage of subjects in each category on the 8-point ordinal scale (time frame: Days 3, 5, 8, 11, 15, 22, and 29) (Phase II, III);
 - Proportion of patients alive and free of respiratory failure up to Day 29 (Phase II, III);
 - Proportion of patients who are discharged from acute care up to Day 29 (Phase II, III);
 - Days of supplemental oxygen (if applicable) up to Day 29 (Phase II, III);
 - Days of non-invasive ventilation/high flow oxygen (if applicable) up to Day 29 (Phase II, III);
 - Days of invasive mechanical ventilation/extracorporeal membrane oxygenation (ECMO) (if applicable) up to Day 29 (Phase II, III);
 - Time to hospital discharge up to Day 29 (Phase II, III);
 - Number and proportion of non-responders having mutations in the gene encoding the SARS-CoV-2 S protein through Day 29. A non-responder is defined as a patient who does not achieve a reduction in viral shedding or

persistence viral presence or have a rebound in viral shedding following suppression (Phase II, III).

- Safety of SCTA01:

- Cumulative incidence of serious adverse events (SAEs) (Phase II, III);
- Cumulative incidence of Grade 1, 2, 3 and 4 clinical and/or laboratory adverse events (AEs) (Phase II, III);
- Discontinuation or temporary suspension of infusions (for any reason) (Phase II, III);
- Chemistries, hematology, urinalysis, coagulation test, IL-6, ferritin, procalcitonin, thrombin time, D-dimer (Phase II, III);
- Number and proportion of patients who are suspected to experience ADE (Phase II, III).

- Virologic efficacy of SCTA01:

- Change from baseline in viral shedding as measured by quantitative reverse transcription polymerase chain reaction (RT-qPCR) in NP or OP swab samples (Phase II, III);
- Time-weighted average change from baseline between SCTA01 group and placebo group in viral shedding as measured by RT-qPCR in NP or OP swab samples (Phase II, III);
- Time to SARS-CoV-2 RNA negative (NP or OP swab samples) as determined by RT-qPCR (Phase II, III).

- Pharmacokinetics (PK) of SCTA01:

- Pharmacokinetic characteristics in severe COVID-19 patients (Phase II).

- Immunogenicity of SCTA01:

- Immunogenicity assessment includes the number and percentage of subjects who develop detectable anti-drug antibodies (ADA) (Phase II, III).

Exploratory Endpoints:

- The correlation between the baseline serological antibody level and therapeutic effect (Phase II, III);
- Quantitative SARS-CoV-2 virus in patient's blood (Phase II, III).

Study Design:

The study is a multicenter, adaptive, randomized, double-blinded and placebo-controlled Phase II/III trial, and will be conducted at selected investigational sites globally. The study is comprised of 2 parts: dose selection (Phase II) and pivotal treatment effect (Phase III).

Phase II part will evaluate the efficacy, safety and PK of SCTA01 15 mg/kg and 50 mg/kg in severe patients with COVID-19. The primary endpoint will evaluate the difference of TTCI among study group 1 [SCTA01 15 mg/kg + best supportive care (BSC)], study group 2

(SCTA01 50 mg/kg + BSC) and control group (placebo + BSC) up to Day 29. The secondary endpoint will evaluate the difference of virologic efficacy among study group 1 (SCTA01 15 mg/kg + BSC), study group 2 (SCTA01 50 mg/kg + BSC) and control group (placebo + BSC) from baseline to Day 8, and then determine the recommended dose of Phase III part.

In the Phase II part of the study, 285 subjects will be randomized by 1:1:1 ratio to 15 mg/kg group, 50 mg/kg group and placebo group, with 95 subjects in each group.

At the end of Phase II part, enrollment will be paused and the interim analysis for dose selection will be performed after the 285th subject has been observed for TTCI. An Independent Data Monitoring Committee (IDMC) will assess the benefit and risk to decide a dose for the Phase III part of the study.

Enrollment will be resumed after the IDMC has completed their evaluation and recommended the dose for the Phase III part.

The Phase III part will evaluate the efficacy, safety, and immunogenicity of SCTA01 at the dose recommended by the IDMC (X mg/kg or X mg) in hospitalized patients with severe COVID-19. The primary endpoint will evaluate the difference of TTCI between study group (SCTA01 X mg/kg or X mg + BSC) and control group (placebo + BSC) up to Day 29.

Approximately 510 subjects in Phase III part will be randomized by 1:1 ratio to SCTA01 (X mg/kg or X mg) group and placebo group, with 255 subjects in each group. IDMC will be used to monitor safety and efficacy of the study.

Total number of Phase II/III study is about 795.

Interim analysis (IA): There will be three un-blinded interim analyses when the 143rd patient in Phase II has completed Day 8 visit, at the end of Phase II and when the 160th patient in Phase III has completed Day 29 or Early Withdraw visit.

- The 1st interim analysis is for safety evaluation. The safety data will be reviewed at the 1st interim analysis, but the preliminary review of efficacy data is supported if early data and external emerging data warrants.
- The 2nd interim analysis is for dose selection: the analysis will be performed at the end of Phase II when the 285th patient completed Day 29 or Early Withdraw visit. The dose selected to continue to the Phase III part will be the dose with the greater effect in reduction of viral load compared to placebo at Day 8. Time to clinical improvement of each dose will be evaluated and the RR threshold of 1.15 will be used as a futility boundary at the end of Phase II. The futility boundary is non-binding, and the IDMC may recommend study continuation even if the futility bound is met on TTCI. If any safety signal is observed for any dose, the IDMC will weigh this information against the efficacy results in selecting the dose for Phase III.
- The 3rd interim analysis is the penultimate analysis that allows for stopping for superior efficacy. It is planned when 160 patients in Phase III (approximately 31% information time of Phase III part, or equivalently 50% of the TTCI events combined from phase II and phase III part of the study) have been documented in the ITT population. If the interim analysis is performed at 31% of information time of Phase III, based on Pocock type boundary of α -spending function, a 1-sided p -value less than 0.01068 using inverse normal

method to combine *p*-value from Phase II part and Phase III part will need to be observed to declare statistical significance. A futility boundary of an observed RR of 1.22 will be used to declare failure of the study when TTCI events from Phase II and Phase III part combined are exactly 280, which is equivalent to an observed one-sided *p*-value of 0.05.

Note: The critical values of nominal *p*-value and hazard ratio that will be used to declare statistical significance and/or futility at the interim analyses will be calculated based on the actual number of the TTCI events documented at the time the interim analysis.

The interim analyses will be performed by an independent statistician external to the study team. The results of the interim analyses will be presented to the IDMC by the independent statistician. The IDMC will provide the Sponsor with a recommendation to continue the trial as planned, to have an interruption, to make a protocol amendment, or to terminate the trial. If the interim analysis demonstrates significantly shortened TTCI in the SCTA01 group compared to the control group, the IDMC could recommend to terminate and un-blind the study, and the study could be announced as completed.

Main Inclusion Criteria:

- Hospitalized patients with severe COVID-19 (5 point on the 8-point ordinal scale). According to the NIH definition, severe patients are those individuals who have one of the following: 1) respiratory rate > 30 breaths per minute 2) SpO₂ ≤ 93% on room air at sea level; 3) PaO₂/FiO₂ < 300 mmHg or SpO₂/FiO₂ ≤ 315 mmHg; 4) lung infiltrates > 50%. In high altitude area (over 1000 meters), PaO₂/FiO₂ should be corrected according to the following formula: PaO₂/FiO₂ × [760/barometric pressure (mmHg)]; 5 point: Hospitalized, requiring supplemental oxygen;
- Male or female adult ≥18 years of age at time of enrollment;
- Has documented laboratory-confirmed SARS-CoV-2 infection as determined by PCR. Note: Patient can be enrolled before SARS-CoV-2 infection has been confirmed and can be tested by any approved clinical test other than PCR as long as SARS-CoV-2 infection is then confirmed by PCR;
- ≤ 14 days since symptoms of COVID-19 onset;
- Eligible COVID-19 vaccinated patients at the time of enrollment are allowed.

Main Exclusion Criteria:

- Patients who need non-invasive ventilation or high flow oxygen (i.e., 6 point on the 8-point ordinal scale);
- Patients with critical COVID-19. According to the NIH definition, critical patients are those individuals who have one of the following conditions: 1) respiratory failure and need invasive mechanical ventilation; 2) septic shock; 3) multiple organ dysfunction;
- Patients with severe COVID-19 who received convalescent plasma or anti-SARS-CoV-2 spike (S) protein targeted therapy;
- Alanine-amino transferase (ALT) or aspartate transaminase (AST) is 5 times higher than the upper limit of the normal value;

- Estimated glomerular filtration rate (eGFR) < 30 mL/min or on dialysis {eGFR calculated by Cockcroft-Gault formula (*Cockcroft DW, 1976*), Male: CrCL (mL/min) = $[(140 - \text{age}) \times \text{weight (kg)}] \times 1 / [\text{SCr (mg/dL)} \times 72]$; Female: CrCL (mL/min) = $[(140 - \text{age}) \times \text{weight (kg)}] \times 0.85 / [\text{SCr (mg/dL)} \times 72]$ }.

Investigational Product, Dosage, and Mode of Administration:

SCTA01 will be provided in glass vial. Each vial contains 10 mL of study medication with a concentration of 25 mg/mL.

Placebo is identical in physical appearance to that of SCTA01 injection and contains the same inactive ingredients which include histidine, sodium chloride, polysorbate 80, hydrochloric acid and injection grade water.

SCTA01/Placebo should be stored under refrigeration at 2~8°C (36-46°F) in the original carton to protect from light and avoid repeated freezing/thawing.

Each participant will receive a single intravenous infusion of either SCTA01 or placebo. Infusion volume will be 500 mL and infusion time is 3 hours (± 0 minutes).

Detailed infusion information will be in the Pharmacy Manual.

Duration of Treatment:

Single dose of drug.

Reference Therapy, Dosage, and Mode of Administration:

Best supportive care is allowed as a base therapy except the use of convalescent plasma, or anti-SARS-CoV-2 spike (S) protein targeted therapy. Refer to local clinical routine for the treatment of patients with severe COVID-19.

Criteria for Evaluation:

Efficacy: 8-Point ordinal scale.

Safety: Division of AIDS (DAIDS) Table for Grading the Severity of Adult and Pediatric Adverse Events (Version 2.1, July 2017).

Statistical Methods:

- All enrolled subjects set: All patients who sign the informed consent form (ICF) will be registered in the electronic data collection (EDC) system. Cases that are included in the study but not administered study drug will be analyzed using this analysis set.
- ITT set: All patients who are randomly assigned to and receive a dose of study drug. This is the primary analysis set for the efficacy analyses, and patients will be analyzed according to the treatment to which they are randomly assigned.
- Full analysis set (FAS): All patients who are randomly assigned, receive a dose of study drug and have at least one primary endpoint measurement. This analysis set will support the robustness of the primary efficacy results and patients will be analyzed according to the treatment to which they are randomly assigned.

- Safety set (SS): All patients who are randomly assigned and receive a dose of study drug. All safety analyses will be based on the safety set, with patients analyzed according to the treatment they received.
- Pharmacokinetics set (PKS): Subjects that receive single-dose investigational drug and have at least one blood-drug concentration data point which can be analyzed. PKS consists of PK Concentration set (PKCS) and PK Parameter set (PKPS).
- Per-protocol set (PPS): All patients in the ITT set without any major protocol deviations which may affect efficacy evaluation. The Per-protocol combined set will be used for sensitivity analysis of the primary endpoint.

Safety Analysis

The safety summaries will include treatment group and placebo group, comprising all patients in the safety set.

Adverse events will be tabulated by treatment group. The number and percentage of patients with at least one AE will be presented along with a breakdown by system organ class and preferred term (PT), with each patient being counted once at each summarization level. This summary will be repeated for treatment-emergent adverse events (TEAEs), AEs that lead to study drug discontinuation, by relationship to study drug, by intensity and for SAEs.

Laboratory test results, vital signs data, and electrocardiogram (ECG) data will be presented in tables summarizing absolute values and change from baseline by treatment group, with shift tables included as appropriate.

Virologic Efficacy Analysis

- Change from baseline in viral shedding as measured by RT-qPCR in NP or OP swab samples (Phase II, III);
- Time-weighted average change from baseline in viral shedding as measured by RT-qPCR in NP or OP swab samples (Phase II, III);
- Time to SARS-CoV-2 RNA negative in NP or OP swab samples as determined using RT-qPCR (Phase II, III).

Recommended Dose for Phase III Analysis

Based on the safety, virologic effect and clinical efficacy of SCTA01 15 mg/kg and 50 mg/kg groups in Phase II part, the dose that will continue to Phase III part will be determined by the effect in reduction of viral load compared to placebo at Day 8 and TTCI of each dose. The dose with greater virologic suppression effect will be selected with no harmful effect of clinical relevancy.

Phase III Clinical Efficacy Analysis

Primary endpoint is TTCI up to Day 29. TTCI is defined as the time (in days) from randomization to the first day on which a patient satisfies point 1, 2, or 3 on the 8-point ordinal scale and maintains a score ≤ 3 at least 48 hours (initial improvement) and maintains this up to Day 29 (sustained improvement).

All deaths up to Day 29 will be considered censored at Day 29. Any subjects that are lost to follow-up or terminated early prior to meeting primary endpoint will be censored at the day of their last observed assessment. Subjects who completed follow-up but do not meet primary endpoint will be censored at the day of their Day 29 visit. The subjects who take prohibited medications before Day 29 will be treated as treatment failures and will be censored at the time of medication use.

The primary analysis uses the stratified log rank test to compare treatment group to control group through Day 29 with respect to TTCl. Covariate factors may include country duration of symptoms prior to enrollment, comorbidity and best supportive treatment. Note that if some strata are too small, they might be combined together to allow statistical method work well.

For each group, the Kaplan-Meier estimate of TTCl survival function will be constructed. Hazard ratio of SCTA01 vs. placebo with two-sided 95% CI will be derived from the stratified Cox proportional hazard model. The number of patients with a TTCl event and number of patients censored for the TTCl analysis will be summarized by treatment group. Percentage of subjects in each category using the 8-point ordinal scale up to Day 29 will also be summarized by treatment group.

PK Analysis

Population pharmacokinetic analysis will be performed using NONMEM® (Version 7.4, Icon Inc, PA, USA)..

Immunogenicity Analysis

To collect the proportion of subjects with anti-SCTA01 antibody and to evaluate the change of anti-SCTA01 antibody in patient serum.

Non-Response to SCTA01 assessments

Number and proportion of non-responders having mutations in the gene encoding the SARS-CoV-2 Spike protein through Day 29. A non-responder is defined as a patient who does not achieve a reduction in viral shedding or persistence viral presence or have a rebound in viral shedding following suppression (Phase II, III).

Stopping Infusion Criteria: If a severe allergic reactions (including anaphylaxis) (Grade 3 or higher) is observed during infusion, the infusion will be immediately stopped and no further SCTA01/placebo treatment will be administered to the subject.

TABLE OF CONTENTS

PROTOCOL SYNOPSIS.....	2
TABLE OF CONTENTS	10
LIST OF TABLES	14
LIST OF FIGURES	15
SCHEMA.....	16
ABBREVIATIONS AND DEFINITIONS OF TERMS.....	17
1. STUDY OBJECTIVES AND ENDPOINTS	19
1.1. Primary Objectives	19
1.2. Secondary Objectives	19
1.3. Exploratory Objectives.....	19
1.4. Primary Endpoints.....	19
1.5. Secondary Endpoints.....	19
1.6. Exploratory Endpoints.....	21
2. BACKGROUND	22
2.1. Spike Protein and SARS-CoV-2	22
2.2. Convalescent Plasma in the Treatment of COVID-19	22
2.3. Potential Efficacy	22
2.4. Booster Neutralizing Antibodies against COVID-19.....	23
2.5. SCTA01 is a Neutralizing Antibody against SARS-CoV-2.....	23
2.6. Preclinical Pharmacokinetics	23
2.7. Preclinical Pharmacodynamics	24
2.8. Preclinical Toxicology	26

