5.6. Randomization and Blinding

Each subject will be assigned a unique identification number. The subject identification (SID) number will be used to identify the subject throughout the study and will be entered on all study documentation. The SID will be an 8-digit number with the first 4 digits corresponding to the site number and the last 4 digits sequentially assigned by the site at screening. If a subject discontinues from the study at any time, his/her study number cannot be reassigned to another subject.

Phase II part of the study: Patients will be randomly assigned to receive SCTA01 (15 mg/kg), SCTA01 (50 mg/kg) or placebo a 1:1:1 ratio. The randomization schedule will be stratified by country.

Phase III part of the study: Patients will be randomly assigned to receive SCTA01 (X mg/kg or X mg) or placebo in a 1:1 ratio. The randomization schedule will be stratified by country.

An interactive web response system (IWRS) will be used to administer the randomization schedule. An independent CRO statistician will generate a permuted block randomization schedule for IWRS, which will link the sequential patient randomization numbers to the treatment codes.

Each patient will be assigned a randomization number which is different from the patient identification number. Once a randomization number has been allocated to a patient, it cannot be assigned to another patient.

To ensure the treatment assignment is unbiased and concealed from all individuals involved in the study, all enrolled patients are randomized to SCTA01 or placebo group using the following procedures: 1) randomization data are kept strictly confidential until the time of final analyses, and will not be accessible to anyone involved in the conduct of the study with the exception of the IDMC team and unblinded statistician; 2) the identity of the treatments will be concealed by the use of study drugs (SCTA01 and Matching Placebo) that are all identical in packaging, labeling, schedule of administration and appearance.

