7.1. Time and Events Schedule

The schedule of study assessments is provided in Tables 2, 3, and 4 below. Flexibility is allowed in scheduling the visits according to visit time windows as specified in table below.

For a procedure required at early withdraw (Table 4), it does not need to be performed if the procedure is not a daily required procedure and it has been done in 3 days before subject's withdraw.

Table 2. Schedule for Screening Visit

Study Process	Screening Period	Comments
Visit	V1	
Visit day	D-3~ D-1	
Informed consent	X	
Demographics	X	Including birth date, sex, race, and ethnicity.
Medical history	X	Medical history prior to signing the ICF including: - The day of onset of COVID-19 signs and symptoms. - History of medication allergies. - History of medical conditions within 30 days prior to signing the ICF including but not limited to chronic oxygen requirement prior to onset of COVID-19. - Ask if they are participating in another clinical trial or plan to enroll in another clinical trial in the next 30 days.
Physical examination	X	Testing items see Section 7.2; Physical examination is focused on lung auscultation.
β-HCG	X	For non-postmenopausal female subjects or who have not undergone surgical sterilization
Serum chemistry	X	Testing items see Section 7.2.
SARS-CoV-2 infection confirmation	X	Has documented laboratory-confirmed SARS-CoV-2 infection as determined by PCR. Note: Patient can be enrolled before SARS-CoV-2 infection has been confirmed and can be tested by any approved clinical test other than PCR as long as SARS-CoV-2 infection is then confirmed by PCR.
Vital signs	X	Include body temperature, pulse rate, blood pressure, respiratory rate in semi-supine position
Diagnosis of severe COVID-19 infection	X	Use one of following criteria: 1) respiratory rate; 2) SpO ₂ ; 3) PaO ₂ /FiO ₂ or SpO ₂ /FiO ₂ ; 4) chest X-ray or CT. Refer to Section 4.1 for details.
8-Point Ordinal Scale	X	
Inclusion/Exclusion criteria review	X	
AEs	X	Record the AEs from after obtaining the Informed Consent
Prior treatments within the last 30 days	X	

Table 3. Schedule for Treatment Visit

Study Process	Treatment Period	Comments
Visit	V2	
Visit day	D1	
Randomization	X	
Height	X	
Weight	X	

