Vital signs	X	Refer to Section 7.2.2. At 15 ± 5 , 30 ± 5 , 45 ± 5 , 60 ± 5 , 90 ± 10 , 120 ± 10 , 150 ± 10 , 180 ± 10 , 240 ± 10 , 300 ± 10 minutes after the beginning of infusion (i.e. every 15 ± 5 minutes for the first hour of infusion, every 30 ± 10 minutes until the end of infusion and every 60 ± 10 minutes for 2 hours after the end of infusion).
Targeted physical examination		Are performed only when needed to evaluate possible adverse events.
12-lead ECG	X	Refer to Section 7.2.3 Test within 2 h (± 10 min) before infusion, and within 2 h (± 10 min) after the end of infusion. Additional ECG examination is at the discretion of the Investigator per standard clinical practice or as clinically indicated.
Hematology	X	Testing items see Section 7.2.5. Sample will be collected before infusion.
Serum chemistry	X	
Urinalysis	X	
Coagulation test	X	
IL-6	X	
Ferritin	X	
Procalcitonin	X	
Thrombin time	X	
D-dimer	X	
Serological samples for anti-spike protein antibodies	X	Blood samples will be collected within 0.5 h (± 5 min) before infusion.
Immunogenicity (ADA) blood samples	X	
PK samples	X	Intensive sampling of Phase II part: - Within 0.5 h (± 5 min) before the beginning of infusion; 1 h (± 10 min) post end of infusion .
Blood for PCR SARS-CoV-2 test	X	Sample will be collected before infusion.

NP or OP swab for SARS-CoV-2 test	X	Sample will be collected before infusion. NP swab preferred. If NP swab cannot be obtained, OP swab may be used.
SpO ₂	X	Record SpO ₂ before infusion, and 1 h (\pm 0 min), 2 h (\pm 0 min), 3 h (\pm 0 min) after the end of infusion. Also record oxygen supplementation: low flow oxygen, high flow oxygen, or other.
8-Point Ordinal Scale	X	To evaluate within 30 ~ 60 min before infusion.
Administration of SCTA01/Placebo	X	The dose should be given within 24 hours after randomization.
AEs	X	
Concomitant medications	X	Items see Section 3.6.1.

Table 4. Schedule for Follow-up Visit

Study Process	Follow-up Period										Comments
	V3	V4	V5	V6	V7	V8	V9	V10	V11	V12	
Visit											
Visit day	D2	D3	D5	D8	D11	D15	D22	D29	D60	D120	
Window period (\pm day)	\pm 0 d	\pm 0 d	\pm 1 d	\pm 1 d	\pm 1 d	\pm 2 d	\pm 3 d	\pm 3 d	\pm 3 d	\pm 7 d	Early Withdraw
Vital signs		Daily until discharge									
Targeted physical examination		Performed only when needed to evaluate possible adverse events									
β -HCG	Only when potential pregnancy is suspected and at the end of the study								X		
12-lead ECG		X		X		X		X		X	
Hematology		X		X		X		X		X	

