7.2.4. SpO₂

Record SpO₂ while participant is at rest, at the same time record oxygen supplementation: low flow oxygen, high flow oxygen, or other. Record FiO₂ if known, and method of delivery, if applicable.

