9.7. Efficacy Analysis

9.7.1. Primary Efficacy Analysis

The primary endpoint is TTCI up to Day 29. TTCI is defined as the time (in days) from randomization to the first day on which a patient satisfies point 1, 2, or 3 on the 8-point ordinal scale and maintains a score ≤ 3 at least 48 hours (initial improvement) and maintains this up to Day 29 (sustained improvement).

All deaths within 29 days or terminated early due to AE will be designated censored at Day 29 with respect to primary endpoint. Any subjects lost to follow-up or terminated early due to other reasons prior to an observed primary endpoint will be censored at the day of their last observed assessment. Subjects who completed follow-up but did not experience a primary endpoint event will be censored at the day of their Day 29 visit. The subjects who take prohibited medications will be regarded as treatment failures and will be censored at the time of medication use.

The primary analysis will use the stratified log rank test to compare treatment group to control group through Day 29 with respect to primary endpoint. Covariate factors may include country, duration of symptoms prior to enrollment, comorbidity and best supportive treatment. Note that if some strata are too small, they might be combined together to allow statistical method work well.

For each group, the Kaplan-Meier estimate of TTCI survival function will be constructed. Hazard ratio of SCTA01 vs. placebo with two-sided 95% CI will be derived from the stratified Cox proportional hazard model. The number of patients with a TTCI event and number of patients censored for the TTCI analysis will be summarized by treatment group.

The sensitivity analyses (such as using different population, different censoring rules and/or different covariates) for the primary endpoint will be fully described in the statistical analysis plan (SAP).

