9.7.7. Sub-group Analyses

Subgroup analyses for the primary outcomes will evaluate the treatment effect across the following subgroups: country, race, ethnic group, duration of symptoms prior to enrollment, age, sex and comorbidity, best supportive treatment. A forest plot will display confidence intervals across subgroups. Interaction tests will be conducted to determine whether the effect of treatment varies by subgroups.

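### The covariates listed for the primary TTCI analysis leave out age and baseline oxygenation, although both are collected; pre-specified adjustment would be a cheap gain in efficiency

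*Combined protocol and SAP*

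**What the plan says.** Section 9.7.1 states: "The primary analysis will use the stratified log rank test to compare treatment group to control group through Day 29". The hazard ratio comes from a stratified Cox model. On covariates it says: "Covariate factors may include country, duration of symptoms prior to enrollment, comorbidity and best supportive treatment". The Synopsis (Phase III Clinical Efficacy Analysis) gives the same four factors: "Covariate factors may include country duration of symptoms prior to enrollment, comorbidity and best supportive treatment". Section 5.6 names one randomisation factor for each phase: "The randomization schedule will be stratified by country".

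Both missing variables are collected:
- **Age.** The demographics row of Table 2 (7.1) reads "Including birth date, sex, race, and ethnicity". Section 9.7.7 makes age a subgroup factor, in the list "country, race, ethnic group, duration of symptoms prior to enrollment, age, sex and comorbidity, best supportive treatment".
- **Oxygenation.** Table 3 (7.1) schedules SpO2 before infusion on Day 1 and adds: "Also record oxygen supplementation: low flow oxygen, high flow oxygen, or other". FiO2 is weaker: 7.2.4 asks for it "if known, and method of delivery, if applicable".

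Section 9.7.1 leaves sensitivity analyses with other covariates to the SAP. It does not say that the primary covariate set will be settled there.

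**The concern.** Every patient enters at ordinal point 5 and randomisation balances only country. Age, and differences in oxygenation within point 5, are therefore handled neither by the design nor by the listed covariates. In a proportional-hazards analysis in which most patients have the event, leaving out a prognostic variable attenuates a non-null rate ratio even when the arms are perfectly balanced, and the test loses efficiency.

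Three things in this trial depend on that estimate or its test: the stage-wise p-values p1 and p2, the efficacy stop at the third interim analysis, and the observed RR set against 1.15 at the end of Phase II and 1.22 at the third interim. At the futility looks the RR is compared with a fixed number, so attenuation moves an effective drug towards a futility call.

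**Working it through.** **Inputs from the documents.** RR 1.4, 80% event rate and power over 90% (9.4); 350 patients per arm and final one-sided level 0.0166 (9.3); 556 events at the final analysis (9.7.6); 149 and 280 events at the two futility looks (Table 7).

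**Step 1: the plan's own figure.** 700 × 0.80 = 560 events, close to 556. Schoenfeld power = Φ(√(d/4) × ln RR − z), with z = 2.130 for 0.0166: √(556/4) × ln 1.4 = 11.79 × 0.3365 = 3.967, and Φ(3.967 − 2.130) = 96.7%. I also simulated the two-stage test: weights √(285/795) and √(510/795), Simes-adjusted Phase II p-value, bounds 0.01068 and 0.0166, futility ignored. It gives about 96% if both doses have RR 1.4 and about 94% if only the selected dose does. The stated power reproduces.

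**Step 2: omit a prognostic score.** Assumption, not in the documents: the omitted variables form a normal score with SD s on the log-rate scale. Times are exponential over 28 days with 80% events, and the conditional RR is 1.4. Information lost is L = 1 − (z omitted / z adjusted)², by numerical integration. Power is Φ(√(556(1 − L)/4) × ln 1.4 − 2.130). Event counts use unrounded losses.

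| s | Rate ratio per SD | Attenuated RR | L | Events of 556 | Power |
|---|---|---|---|---|---|
| 0 | 1.00 | 1.400 | 0 | 0 | 96.7% |
| 0.1 | 1.11 | 1.397 | 1.2% | 7 | 96.5% |
| 0.2 | 1.22 | 1.389 | 4.6% | 25 | 96.0% |
| 0.3 | 1.35 | 1.377 | 9.7% | 54 | 94.9% |
| 0.4 | 1.49 | 1.361 | 16.0% | 89 | 93.4% |
| 0.6 | 1.82 | 1.326 | 29.7% | 165 | 88.4% |

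**Step 3: check by simulation.** With 350 per arm and 8 country strata (an assumed number), mean z unadjusted against adjusted for an age score was 3.81 against 3.90 (s = 0.2), 3.77 against 3.95 (0.3) and 3.49 against 3.81 (0.4). Then 1 − (3.81/3.90)² = 4.6%, 1 − (3.77/3.95)² = 8.9% and 1 − (3.49/3.81)² = 16.1%, in line with the table. Splitting age at its median as an extra stratum recovered less than half of the gain, hence the preference for continuous age.

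**Step 4: power in the two-stage test.** With both doses at 1.4, applying L from step 2 gives 95.6%, 94.5% and 92.8% for s = 0.2, 0.3 and 0.4, against 96.4% without loss. If only the selected dose works, the figures are 92.7%, 91.2% and 89.1%, against 93.8%.

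**Step 5: where 90% is crossed.** 90% power at 0.0166 needs 412 events, so the loss would have to reach 1 − 412/556 = 25.9%, or s of about 0.54.

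**Step 6: futility looks.** The chance that an effective drug falls below cut-off c is about Φ((ln c − ln RR) × √d / 2), each look taken alone, using the attenuated RR from step 2.
- c = 1.15, d = 149: 11.5% at RR 1.400; 12.5%, 13.6% and 15.2% for s = 0.2, 0.3 and 0.4.
- c = 1.22, d = 280: 12.5% at RR 1.400; 13.9%, 15.6% and 18.0%.

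**Step 7: if 1.4 is already the marginal RR.** The conditional RR is then 1.414, 1.425 or 1.455 for s = 0.22, 0.30 or 0.45. Adjusted power is 97.4%, 98.0% or 98.9%, against 96.7% unadjusted.

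**The case against.** A stratified log-rank test is a valid, conventional primary analysis that needs no covariate model. Attenuation from an omitted covariate is non-collapsibility, that is, a different estimand and not bias. At RR 1 there is none, so type I error and the no-effect column of Table 7 are untouched. All of this stands, and it limits the point to efficiency.

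Several stronger readings are tempting but unsupported:
- **A reader might infer that age and oxygenation are ruled out.** The list is permissive, so they are only unnamed. That openness does not remove the point, because the primary set still has to be fixed and the text gives no sign that these two would be in it.
- **A reader might infer that a known share of the events is lost.** The documents give no prognostic strength; the loss follows from the SD chosen. Only age was simulated, against country strata alone. Comorbidity may absorb part of the age effect, and restriction to point 5 narrows oxygenation.
- **A reader might put the loss at s = 0.4 at 19%.** That is (3.81/3.49)² − 1, the gain relative to the unadjusted test. The share lost is 16%.
- **A reader might infer that SpO2/FiO2 is available for everyone.** It is not assured, since FiO2 is recorded only where known. SpO2 with type of support is scheduled for all. Type of support will vary little at entry, because patients needing high-flow oxygen are excluded, so much of the gain may come from age.

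**Conclusion.** The point holds as a cheap improvement. Two baseline variables that are scheduled for every patient are missing from the listed primary covariates. If they are prognostic, the trial forgoes about 5%, 9-10% or 16% of its information at an assumed SD of 0.2, 0.3 or 0.4 (about 1% at 0.1, 30% at 0.6), and less to the extent that comorbidity stands in for age. The chance of a false futility reading rises by about 1 to 5 percentage points at either look.

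A reader might conclude that the trial is underpowered. The documents do not support that. Over SDs of 0.2 to 0.4, power is about 93-96% unadjusted against about 96-97% adjusted, where 9.4 promises over 90%. The one exception in that range is the two-stage test at SD 0.4 with only the selected dose active, at about 89%. Section 9.4 takes its RR from an earlier trial's point-5 patients without saying whether it was covariate-adjusted. If 1.4 is a marginal RR, no planned power is lost and adjustment only adds to it.

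**What to change.** In the Synopsis and 9.7.1, before any unblinding, replace the open list with a fixed primary model:
- Country as the stratum, with continuous age and baseline (pre-infusion) SpO2 plus type of oxygen support as covariates in the stratified Cox model. Do not use SpO2/FiO2.
- p1, p2, the reported rate ratio and the RR used at the futility looks all taken from that model.
- A simple stated rule for missing baseline values, so that no patient drops out of the confirmatory test.
- A statement of whether symptom duration, comorbidity and best supportive treatment stay in the model.
- The country-stratified log-rank test kept as a sensitivity analysis.

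The cost is wording only, with no new data and no added patients. With the model fixed in advance, type I error is not affected. The small downsides are that the rate ratio becomes conditional on these covariates and that the primary test depends on a covariate model.
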